of other existing methods such as invasive methods.[47] The Esophageal Cooling Device (shown in Figure 1 and Figure 2) is a multichambered silicone heat exchanger that is placed in the esophagus to provide highly efficient heat transfer to/from a patient while simultaneously maintaining access to the stomach to allow gastric suctioning, decompression, and drainage, as usually performed in such patients in emergency departments, operating rooms, and intensive care units.

[figure not shown]

Figure 1. Photograph of the Esophageal Cooling Device (ECD).

The esophagus is in close proximity to blood flow from the heart and great vessels, and the Esophageal Cooling Device is designed to take advantage of this heat exchange environment. The Esophageal Cooling Device's ability to decompress the stomach and avoid distention of the esophagus away from the device ensures good contact with the esophageal mucosa, and thus maximizes heat transfer from the patient. The Esophageal Cooling Device replaces the standard orogastric tube which is placed in the target patient population as a routine standard of care, is made of standard medical-grade silicone, and is generally similar in size and shape to the orogastric tubes currently used. Initial mathematical and animal studies have shown strong support for the efficacy and safety of the Esophageal Cooling Device.[47-49]

[figure not shown]

Figure 2. The Esophageal Cooling Device (ECD) shown in place in the esophagus (replacing the routine gastric tube placed in the target population as a standard of care), and located behind the trachea (containing the endotracheal tube which is placed in the trachea routinely to provide ventilation in the target patient population).

Study design:

Prospective, interventional study evaluating the feasibility and safety of the Esophageal Cooling Device in 15 patients suffering from traumatic brain injury and treated with targeted temperature management. Comparison of outcomes will be made to historical controls, and analysis will utilize a non-inferiority design.

Primary outcome:

Time to initiation of targeted temperature management, as measured from the time a decision is made to begin targeted temperature management, to the time the esophageal cooling device is in place.

Secondary outcomes:

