After the first 24 hours from the admission of the patient to the hospital Simplified Acute Physiology Score (SAPS) III will be measured.

Daily during day 1-7 if ICU stay the following procedures and assessments will be performed and recorded in the CRFs:

- Sequential Organ Failure Assessment (SOFA) scores;
- GCS scores;
- Pupillary and corneal reflex check;
- Highest body temperature;
- Highest dose and type of vasopressor/inotropic medication;
- The need for pacing;
- Intracranial pressure monitor pressures will be recorded (if measured);
- Recording of a need for mechanical circulatory assistance;
- Mechanical ventilation (if necessary);
- Recording of daily net fluid balance;
- Recording of adverse events;

Daily from day 8 to ICU discharge or day 14 the following records will be made:

- Patient comatose (yes or no);
- Mechanical ventilation (yes or no);
- Renal replacement therapy (yes or no);
- Presence of pneumonia (aspiration/non-aspiration) and sepsis (yes or no)

CPC should be assessed and recorded daily with the last recording being either at discharge, or at the 30 day time point.

Daily from day 1 to day 14 “do not attempt resuscitation order” should be recorded in the CRFs.

Based on investigator’s discretion, the following procedures may be performed if a decision is being contemplated for withdrawal of patient care”:

- Results and time of SSEP, if performed (n20 present bilaterally/n20 present unilaterally/n20 absent);
- Results and time of EEG, if performed.

At ICU discharge or 30 days from admission the following procedures will be recorded if performed (only CPC and GCS are mandatory):

- EEG, MRI, CT (if performed)
- CPC and GCS;

- Esophagogastroduodenoscopy (if performed)

Throughout the entire study:

- Concomitant medications;
- Adverse events

Statistical analysis

Sample size for primary outcome is calculated with an assumption of time to initiate cooling being approximately 5 minutes, with standard deviation of 4 minutes for the esophageal cooling device, and 20 minutes, with standard deviation of 15 minutes, for alternative devices. A power of 80%, and alpha of 5%, yields a sample size of 14 patients (with an equivalent size of historical controls). Sample size for secondary outcome is calculated for a non-inferiority test against the

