current standard (cooling blankets or evaporative cooling). For the endpoint of percent of time over the study period within 1°C of goal temperature (33°C), the treatment effect of the active control is large, since non-treatment results in essentially no attainment of goal temperature. An estimate of effect of the active comparator (M_1) is therefore greater than would be acceptable to use as a base for a non-inferiority margin. Consequently, a more restrictive non-inferiority margin (M_2) is then proposed of 15% (i.e., if the standard maintains goal temperature $+\/-1^\circ\text{C}$ for 60% of the time, and the ECD maintains goal temperature $+\/-1^\circ\text{C}$ for 85% of the time, the lower bound of the 95% CI on the difference between percent time at goal temperature between standard and test device is greater than 70%). Setting the type I error rate to 5%, for an alpha of 0.05, and a power of 80%, for a beta of 0.2, yields a sample size estimate of 15 patients in the study (with another at least 15 patients coming from historical controls with available esophagogastroduodenoscopy evaluation).

Data analysis: as recommended by current FDA guidance documents, both per-protocol (as-treated) and intent-to-treat analyses will be performed.[53] Lower 95% confidence limit for difference between groups must exclude the non-inferiority margins for primary end point in both efficacy and safety.

Abbreviation

ACT - Advanced Cooling Therapy

AE – adverse event

BNP - brain natriuretic peptide

ECG - electrocardiogram

GCS – Glasgow Coma Score

CPC - Cerebral Performance Category

CT – computed tomography

ECD - Esophageal Cooling Device

ECLS - Extra-Corporeal Life Support

EEG – electroencephalogram

LBBB - left bundle branch block

MAP – mean airway pressure

MRI - Magnetic Resonance Imaging

Protocol No ACT TBI-01

Version No 2.0 dated on 08-Dec-2014

OTC – over-the-counter

ROSC - Return of Spontaneous Circulation

SAE – Serious Adverse Event

SAPS – Simplified Acute Physiology Score

SOFA – Sequential Organ Failure Assessment

SSEP - Somatosensory evoked potentials

STEMI - ST-elevated myocardial infarction

TH - Therapeutic Hypothermia

References:

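### The primary-outcome sample size of 14 does not follow from the stated means, SDs, 80% power and 5% alpha; on those inputs it is larger than needed

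*Combined protocol and SAP*

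**What the plan says.** The first calculation under Statistical analysis concerns the primary outcome. For the device it assumes "time to initiate cooling being approximately 5 minutes, with standard deviation of 4 minutes for the esophageal cooling device". The assumption for the comparator is a mean of "20 minutes, with standard deviation of 15 minutes, for alternative devices". It then states: "A power of 80%, and alpha of 5%, yields a sample size of 14 patients", to be compared "with an equivalent size of historical controls". It names no test, does not say whether alpha is one- or two-sided, and mentions no dropout allowance.

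Three other statements bear on it.

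- The Abstract and the Study design section say that the "analysis will utilize a non-inferiority design".
- The data-analysis paragraph sets the decision rule: "Lower 95% confidence limit for difference between groups must exclude the non-inferiority margins for primary end point". No margin in minutes is given. The only numerical margin, 15%, belongs to the secondary outcome of percent of time near goal temperature.
- The enrolment target of 15 comes from the calculation for that secondary outcome, which "yields a sample size estimate of 15 patients in the study".

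**The concern.** The sentence gives two means, two SDs, a power, an alpha and an equal allocation, which is nearly everything a two-group calculation needs. A reader should be able to recover 14 from it and cannot. The gap is 3 to 5 patients per group on a base of 9 to 11, which is too large for rounding.

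This is the only quantitative justification for the primary outcome. The possible explanations also point in different directions. If the printed SDs were used, the comparison has well over 80% power and the stated power is wrong. If the larger SD was applied to both groups, the SD of 4 was not used, and whether 80% is reached depends on a sidedness that the plan does not state.

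**Working it through.** **Inputs (all from Statistical analysis).** Device: mean 5, SD 4. Alternatives: mean 20, SD 15. Difference 20 − 5 = 15 minutes. Sum of variances 4² + 15² = 16 + 225 = 241. Power 80%, alpha 5%, allocation 1:1. Both sidednesses were tried because none is stated.

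**Step 1. Attempt to reproduce 14 from all stated inputs.**

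Normal formula, per group: n = (z_α + z_β)² × (SD₁² + SD₂²) / difference².

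- Two-sided: (1.960 + 0.842)² × 241/225 = 8.41, so 9.
- One-sided: (1.645 + 0.842)² × 241/225 = 6.62, so 7.

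t tests (noncentral t; Welch degrees of freedom from the two stated SDs):

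| n per group | Pooled t, two-sided | Welch t, two-sided |
|---|---|---|
| 9 | 0.777 | 0.734 |
| 10 | 0.824 | 0.789 |
| 11 | 0.862 | 0.833 |
| 14 | 0.936 | 0.921 |
| 15 | 0.951 | 0.939 |

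So 80% power needs 10 (pooled) or 11 (Welch) per group two-sided. One-sided, either t test needs 8.

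A simulated two-sided Mann–Whitney test on normal data needs about 11 (power 0.81 at 11, 0.88 at 14). On lognormal data with the same means and SDs it already exceeds 0.90 at 7.

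No variant that keeps every stated input gives 14. The stated figure exceeds the two-sided requirement by 14/11 = 1.27 to 14/9 = 1.56, that is, by 27% to 56%.

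**Step 2. What does give 14?**

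- *95% power, normal formula, two-sided:* (1.960 + 1.645)² × 241/225 = 13.92, so 14.
- *90% power, Welch t, two-sided:* 0.898 at 13 and 0.921 at 14, so 14.
- *SD 15 in both groups, one-sided t test, 80% power:* 0.797 at 13 and 0.824 at 14, so 14. This drops the stated SD of 4. With the same SDs the normal formula gives 13 one-sided (12.4) and 16 two-sided (15.7), and the two-sided t test gives 17.
- *Unstated dropout allowance:* 11/0.80 = 13.75 or 10/0.75 = 13.3, both rounded up to 14.

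A non-inferiority margin in minutes cannot explain 14. It would add to the assumed 15-minute advantage and so lower the required number.

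**Step 3. Why it matters which route was used (t-test power).**

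| Assumed SDs | Sidedness | 14 per group | 15 per group |
|---|---|---|---|
| 4 and 15 | two-sided | 92–94% | 94–95% |
| 4 and 15 | one-sided | 96–97% | 97–98% |
| 15 and 15 | two-sided | 72% | 75% |
| 15 and 15 | one-sided | 82% | 85% |

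**The case against.** The strongest reply is that 14 can be reached at the stated 80% power and 5% alpha. A cautious planner might apply the larger SD to both groups and use a one-sided t test, which gives exactly 14. One-sided testing is plausible here, since the plan declares non-inferiority and states its rule in terms of one confidence limit. On that reading the power figure is right and only the method is under-reported. An omitted dropout allowance would be a similar gap in reporting.

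This stands as a possible explanation, and it rules out saying that the 80% must be the wrong number. It does not rescue the sentence. The plan gives an SD of 4 for the device as an input to this calculation, and this route does not use it. The dropout route adds an input that the plan does not mention.

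The second reply is that nothing turns on the figure: 14 exceeds the 9 to 11 needed, and the secondary outcome sets enrolment at 15. That is correct on the printed inputs and is why the point is minor. It is not fully reassuring, because the margin of safety depends on the printed SDs being the ones intended.

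A reader might infer that the primary comparison is underpowered. The documents do not support that: on the assumptions they print, 14 or 15 per group is more than enough. A reader might equally infer that 90% or 95% power was the real target. That too is only one of several routes to 14, and nothing in the plan selects it.

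**Conclusion.** Wrong as written, but minor and conservative on the printed inputs. The stated means, SDs, power and alpha require 9 to 11 patients per group two-sided, or 7 to 8 one-sided, not 14. At 14 per group the two-sided t-test power is 92–94%, not 80%.

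This rests on a comparison of two independent groups of equal size, testing for a difference in means, with both printed SDs. Which element of the sentence is misreported or missing (power, SDs, sidedness, test or attrition) cannot be settled from the documents. The answer decides whether 15 per group gives about 94% power (printed SDs, two-sided Welch t) or about 75% two-sided and 85% one-sided (SD 15 in both groups).

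**What to change.** Correct the sentence so that sample size, power and inputs agree, and name the test and sidedness.

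- If the printed SDs are the ones intended, restate it as: *With means 5 (SD 4) and 20 (SD 15) minutes and two-sided alpha 5%, 80% power needs 11 per group (Welch t); the planned 15 per group gives about 94%.*
- If a common SD of 15, a one-sided test, another power or a dropout allowance was used, state that input and the power that 15 per group gives under it. The 94% must not be carried over to that case.

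The cost is one sentence in the Statistical analysis section. Enrolment stays at 15.

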- Concomitant medications;
- Pre-hospital data: scene of injury (place of residence/public place/other), witness injury (yes/no), time from emergency call to arrival of EMS personnel, estimated time from injury to basic life support, estimated time from injury to advanced life support, location patient intubated (on scene/in ambulance/in emergency department);
- First recorded temperature and method of temperature measurement;
- Glasgow Coma Score;
- Presence of pupillary and corneal reflex;
- Any sign of spontaneous breathing/agonal breathing/gasping at admission;
- Blood gas and FiO₂ (pO₂, pCO₂, BE, pH, lactate);
- Blood glucose;
- Troponin; (if obtained)
- BNP; (if obtained)
- ECG (normal/STEMI/LBBB/other);
- Echocardiogram (EF-normal, EF-moderately impaired, EF-severely); (if obtained)
- Head CT scan (at least the type of injury (subdural, epidural, subarachnoid, etc.) and relevant parameters for each (size, midline shift, volume of hematoma, etc.) should be recorded)
- Surgical interventions (if any)

After screening, subjects eligible for the study participation will undergo the following procedures during this time period:

- Temperature will be measured every hour from time point “0” to 39 hours. Time point “0” is the time either the patient or patient's legal representative, or close relatives signs the consent form. Method of temperature measurement should be recorded for each measurement. Two methods should be used for each time point measurement: 1) standard monitored route (rectal, Foley, intravascular, etc.); 2) temperature reported from the Blanketrol II
- Blood glucose and dose of insulin: 0 hr, 4 hr, 16 hr, 28 hr, 36 hr;
- Lowest and highest heart rate: 0 hr, 4hr, 16 hr, 28 hr, 36 hr;
- Lowest and highest mean arterial pressure: 0 hr, 4hr, 16 hr, 28 hr, 36 hr; (if arterial pressure is measured)

- Dose of vasopressor or other inotropic medication: 0 hr, 4hr, 16 hr, 28 hr, 36 hr;
- PaO₂, FiO₂ and mean airway pressure (MAP): 0 hr, 4hr, 16 hr, 28 hr, 36 hr;;
- Anti-shivering therapy administered, type and dose: 0 hr, 4hr, 16 hr, 28 hr, 36 hr;
- Central venous or mixed venous oxygen saturation: 0 hr, 4hr, 16 hr, 28 hr, 36 hr; (if measured)
- Arterial or venous lactate concentration: 0 hr, 4hr, 16 hr, 28 hr, 36 hr; (if measured)
- Blood gases (pH, pCO₂, pO₂, BE): 0 hr, 4hr, 16 hr, 28 hr, 36 hr; (if obtained as part of routine care)

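### The primary comparison is sized with only as many historical controls as ECD patients, and the plan gives no source, period or eligibility rule for controls and no adjustment

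*Combined protocol and SAP*

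**What the plan says.** Under Study design: "Comparison of outcomes will be made to historical controls", with a non-inferiority analysis. The Randomization section states that there is none.

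The Statistical analysis section sizes two endpoints.

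- **Primary (time to initiation).** The ECD is assumed to have a mean of 5 minutes and an SD of 4. The assumption for the comparator is "20 minutes, with standard deviation of 15 minutes, for alternative devices". The result is "A power of 80%, and alpha of 5%, yields a sample size of 14 patients"; the number of controls is then given in parentheses as "with an equivalent size of historical controls".
- **Secondary (percent of time within 1°C of goal).** The comparator is the "current standard (cooling blankets or evaporative cooling". The calculation gives 15 ECD patients and sets 15 as a floor for historical controls, who must also have an endoscopic evaluation available.

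Available endoscopy is the only condition placed on controls anywhere, and it is attached to the secondary calculation. The analysis paragraph names per-protocol and intent-to-treat analyses and a lower 95% limit rule. It mentions no matching, covariate or sensitivity analysis for confounding. Yet the list under Screening on Day 1 includes body weight, Glasgow Coma Score (GCS) and "First recorded temperature and method of temperature measurement".

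**The concern.** Every between-group statement in this study depends on a control group that the plan does not define. There are two consequences.

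**Precision.** In a single-arm study with historical controls, the number enrolled limits the treated group, whereas the number of controls is limited only by suitable charts. Matching the control number to the enrolled number gives up precision in the group where the plan expects the most scatter.

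**Comparability.** With no source, period or eligibility rule, the choice of controls stays open until outcomes are known. With no pre-specified adjustment, so does the handling of case mix. The generic wording for the primary comparator may or may not mean the same patients as the blanket or evaporative group named for the secondary. The endoscopy condition may also select: in the adverse event definitions, endoscopy for esophageal injury and esophagitis is done where warranted or indicated. If controls were examined on that basis, those with endoscopy would tend to be patients with suspected esophageal problems.

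**Working it through.** **Inputs** (Statistical analysis): ECD mean 5, SD 4; control mean 20, SD 15; difference 15 minutes; power 80%; alpha 5%, sidedness not stated; 14 per group.

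**1. The plan's own figure.** For two means with unequal variances, n per group = (4² + 15²)(z_α + z_β)²/15².

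- Two-sided: 241 × (1.960 + 0.842)²/225 = 8.41, so 9.
- One-sided: 241 × (1.645 + 0.842)²/225 = 6.62, so 7.

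Using t instead of z gives 10 or 8 (pooled) and 11 or 8 (Welch). The stated 14 is therefore not reproduced. It does arise with SD 15 in both groups (one-sided t, 13.1), at 95% power two-sided (13.9), or as a total of 7 + 7. Read as 14 per group it is conservative: two-sided power for a 15-minute difference is about 92% (Welch) to 95% (normal).

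The secondary figure is reproduced if percent of time is treated as a proportion, at one-sided 5%: (0.60 × 0.40 + 0.85 × 0.15)(1.645 + 0.842)²/(0.25 + 0.15)² = 14.2, so 15.

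**2. Where the variance lies.** At 14 and 14, variance = 16/14 + 225/14 = 1.14 + 16.07 = 17.21. The control share is 225/241 = 93%.

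**3. Effect of more controls.** SE = √(16/14 + 225/m), with the Welch t quantile:

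| Controls m | SE (min) | Welch df | 95% half-width (min) | Change |
|---|---|---|---|---|
| 14 | 4.15 | 14.8 | 8.85 | – |
| 28 | 3.03 | 33.8 | 6.16 | 30% narrower |
| 42 | 2.55 | 52.8 | 5.11 | 42% narrower |

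With 15 ECD patients, the number to be enrolled, the half-widths at 15, 30 and 45 controls are 8.50, 5.93 and 4.93. The gain depends on the control SD being much the larger. If both SDs were 15, the normal half-widths at 14, 28 and 42 controls would be 11.1, 9.6 and 9.1, which is 13% and 18% narrower.

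**4. What more controls cannot do.** Suppose there is no true difference, but the control set is biased in the ECD's favour by an assumed amount. The chance that the two-sided 95% interval falsely shows the ECD faster (nominal 2.5%) is:

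| Assumed bias (min) | 14 controls | 28 controls | 56 controls |
|---|---|---|---|
| 3 | 10% | 16% | 26% |
| 5 | 20% | 36% | 58% |
| 10 | 62% | 89% | 99% |

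A larger pool chosen without a rule only makes a biased answer look firmer. Number and selection rule have to be fixed together.

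**The case against.** The strongest reply is that the plan loses little here. On its own assumptions, 14 and 14 gives 92% to 95% power, and the expected interval is roughly 6 to 24 minutes (15 ± 8.85), clear of zero. This stands. The plan gives no margin in minutes for the primary outcome, so a reader who infers that the comparison is too imprecise for its decision goes beyond the documents. The precision gain is an efficiency point.

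Three other readings are tempting and are not supported.

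- **That controls are hand-picked, or that an unadjusted analysis is prescribed.** The plan is silent on both. Silence shows that no rule exists, not which practice will be followed.
- **That the two endpoints have different comparators.** The primary's wording is generic and could include blankets and evaporative cooling. The documents do not say whether the control sets are the same.
- **That the control number is capped throughout.** For the secondary endpoint, 15 is already a floor. The equal-size wording belongs to the primary calculation.

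It is also fair to say that no larger pool is documented, that the endoscopy condition could shrink one, and that old charts may lack weight, first temperature or the time of the cooling decision. These points stand, and they make the gain conditional.

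Finally, adjustment does little for the primary outcome: nothing in the plan suggests that weight or first temperature drives the time from decision to placement. The primary's end event is also the ECD being in place, with no equivalent defined for controls. Neither more controls nor covariates repair that.

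**Conclusion.** The point holds as a design weakness that is cheap to improve; it is not an error that invalidates the study. For the primary outcome, the control group is set equal to the treated group although it carries 93% of the variance under the plan's SDs. For every comparison, the origin of the controls and the handling of case mix are unspecified, apart from available endoscopy. Comparability is the more serious half.

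If 28 or 42 suitable controls exist, the half-width falls from 8.9 to 6.2 or 5.1 minutes with no further enrolment. That rests on the plan's SDs of 4 and 15, on 14 ECD patients and on a Welch interval, and the gain shrinks if the ECD times vary as much as the controls'. The bias figures rest on assumed biases of 3, 5 and 10 minutes. The documents give no basis for the actual bias, so those figures only illustrate that it would not shrink as controls are added.

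**What to change.** Amend the Statistical analysis section before any control data are extracted.

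1. **One pool for the primary and percent-time endpoints.** Take all available consecutive patients with traumatic brain injury from the same ICUs who meet the trial's own eligibility criteria and were cooled with the named standard (blankets or evaporative cooling) in a period fixed in advance. Keep 15 as a minimum for both endpoints.
2. **Endoscopy.** Apply the available-endoscopy condition only to the esophageal safety comparison.
3. **Analysis.** Report the crude difference and, beside it, a pre-specified adjusted one: body weight and first temperature for the temperature endpoints, and GCS as a sensitivity analysis, where the control charts hold these values. State how many controls lack them.
4. **Primary end event.** State which event in a control corresponds to the ECD being in place; without it the primary difference is undefined for any pool.

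The cost is more chart abstraction, a short analysis paragraph and a few degrees of freedom in the adjusted model. No patient is added and treatment does not change. If fewer than 15 controls qualify, that should be known before the comparison is relied on.

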Secondary performance outcomes include the feasibility of inducing, maintaining, and rewarming patients from targeted temperature management using the Esophageal Cooling Device. Specifically, cooling rate, rewarming rate, and the percent of time during the goal-temperature maintenance period within 1°C of goal temperature (typically 33°C, but with some centers using anywhere from 32°C to 36°C) will be measured.

Secondary safety outcomes include evaluation of adverse events including the following: cardiac arrhythmias, severe bradycardia, myocardial infarction/re-infarction, dysphagia, odynophagia, aspiration pneumonia, non-aspiration pneumonia, reflux, esophageal injury, and esophagitis.

Specific definitions of adverse events and the methods used to identify and diagnose each during the treatment and 30-day follow-up phases are as follows:

- Cardiac arrhythmias - recording of atrial or ventricular arrhythmias during course of treatment.
- Severe bradycardia - heart rate < 30/min and necessitating pacing and cessation of TH.
- Myocardial infarction - universal definition of myocardial infarction as per the joint ESC/ACCF/AHA/WHF Task Force for the Redefinition of Myocardial Infarction.[50]
- Dysphagia - report from patient of difficulty in swallowing for more than 24 hours after cessation of device use, diagnosed with a Modified Barium Swallow Study, Videofluoroscopic Swallow Study, or patient self-report.
- Odynophagia - report from patient of pain with swallowing for more than 24 hours after cessation of device use, diagnosed by subjective patient sensation.
- Aspiration pneumonia - demonstration by chest X-ray of evidence of aspiration pneumonia, as diagnosed by treating physician, within 24 hours of cessation of device use.

- Non-aspiration pneumonia - demonstration by chest X-ray of evidence of pneumonia within 24 hours of cessation of device use that is diagnosed by the treating physician as non-aspiration pneumonia.
- Reflux - report of symptoms from patient within 3 days of recovery, with diagnosis via esophageal pH monitoring or endoscopy.
- Esophageal injury - evidence of traumatic and/or ischemic esophageal injuries diagnosed by gastroenterologist evaluation via esophagogastroduodenoscopy as warranted or indicated, and describing the absence of necrosis or not according to the Zargar classification used for caustic injuries within 3 days of recovery .

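### The worked non-inferiority threshold for percent time at goal, a lower bound on the difference above 70%, cannot be met with the plan's own 60% standard and does not follow from its 15% margin

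*Combined protocol and SAP*

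**What the plan says.** All of this is in the Statistical analysis section of the combined protocol and SAP, in the text on sample size for the secondary outcome, unless noted.

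- **Endpoint:** "percent of time over the study period within 1°C of goal temperature (33°C"), tested for non-inferiority against cooling blankets or evaporative cooling.
- **Margin:** "a more restrictive non-inferiority margin (M_2) is then proposed of 15" per cent. The text does not say whether this is absolute or relative.
- **Worked example, in brackets after the margin:** the standard holds goal temperature for 60% of the time and ECD for 85%, and the "lower bound of the 95% CI on the difference between percent time at goal temperature between standard and test device is greater than 70" per cent.
- **Error rates and size:** "Setting the type I error rate to 5%, for an alpha of 0.05, and a power of 80%, for a beta of 0.2", which "yields a sample size estimate of 15 patients in the study", "with another at least 15 patients coming from historical controls". Sidedness, method and standard deviation are not given.
- **Closing rule, in the Data analysis paragraph:** "Lower 95% confidence limit for difference between groups must exclude the non-inferiority margins for primary end point in both efficacy and safety". Its form is suitable, but it is worded for the primary end point, which is time to initiation of temperature management.

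**The concern.** The bracketed example is the only place where the margin is turned into a numerical decision threshold, and this is the only endpoint with a numerical margin. The number printed cannot be a threshold on the difference. An analyst who follows the margin and one who follows the example would apply different criteria and could reach opposite conclusions from the same data. The comparison is with historical controls and is not randomized, so a criterion settled after the data are seen would be hard to defend.

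**Working it through.** **Inputs (Statistical analysis section):** standard 60%, ECD 85%, margin 15%, alpha 0.05, power 80%, 15 ECD patients and at least 15 historical controls.

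**1. The plan's sample size.** The plan names no formula. One that reproduces its figure treats 60% and 85% as proportions (unpooled variance, normal approximation, equal groups):

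n = (z_α + z_0.80)² × [0.60×0.40 + 0.85×0.15] / (0.25 + m)², where m is the margin and the variance term is 0.240 + 0.1275 = 0.3675.

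| Margin | One-sided 5%: (1.645+0.842)² = 6.183 | Two-sided 95% CI: (1.960+0.842)² = 7.849 |
|---|---|---|
| 15 points absolute, (0.40)² = 0.1600 | 14.2 → **15** | 18.03 → 19 |
| 15% relative: 0.15×60 = 9 points, (0.34)² = 0.1156 | 19.65 → 20 | 24.95 → 25 |

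Within this formula, the plan's 15 matches an absolute 15-point margin at one-sided 5%.

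**2. The printed threshold.**

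- Difference in the plan's own scenario: 85 − 60 = 25 points.
- Largest possible difference with the standard at 60%: 100 − 60 = 40 points.
- A lower confidence bound lies at or below the point estimate, so a bound above 70 is out of reach. A difference above 70 would need the standard below 100 − 70 = 30%, half the plan's figure.
- Reversing the sign (standard minus ECD) gives −25, further away.

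This step uses only subtraction and does not depend on standard deviation, sidedness or method.

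**3. What the margin implies.** For ECD minus standard, the lower limit must be above −15 points if the margin is absolute, or above −9 if it is relative. In the plan's scenario with 15 per group, treated as proportions, the standard error is √(0.3675/15) = 0.1565. The expected two-sided 95% lower limit is 25 − 1.96×15.65 ≈ −5.7 points, which clears −15 and is far from 70.

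**4. Power with 15 per group, same formula, margin 15 points.** Power = Φ(0.40/0.1565 − z_α) = Φ(2.556 − z_α). At one-sided 5% this is Φ(0.911) = 82%. With a two-sided 95% CI it is Φ(0.596) = 72%.

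**5. Does n=15 identify the intended reading?** Percent time is a continuous value for each patient. Using the t distribution, 80% power and 15 patients (per group, or ECD alone in the last row), the standard deviation that makes 15 sufficient is:

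| Reading | SD, two-sided 95% CI | SD, one-sided 5% |
|---|---|---|
| 15-point margin, equal performance | 14.2 | 16.1 |
| 9-point margin, equal performance | 8.5 | 9.7 |
| Lower bound on ECD alone above 70%, true ECD 85% | about 19 | about 22 |

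These standard deviations are back-calculated; the plan states none. Each reading can give 15, so n=15 does not settle which was meant.

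**The case against.** **The 70% may be a limit on ECD's own percent time.** It equals 85 − 15, so the margin may have been taken off the ECD value; that is an inference. Under the proportions formula such a bound would need 6.183×0.1275/0.15² = 35.03, so 36 ECD patients. With a continuous outcome, however, 15 could suffice (step 5), so the sample size does not rule this reading out. The text does count against it: the sentence puts the bound on the difference, and 70% is 10 points above the 60% standard, which is a superiority requirement and not a non-inferiority test.

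**The margin is already prespecified and this is only an example.** It is true that 15% is stated, that the endpoint is secondary in a 15-patient feasibility and safety study, and that the closing rule has a usable form. That limits the consequence. It does not remove the contradiction, because the example is introduced as an explanation of the margin and the closing rule is worded for the primary end point.

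**Stronger inferences to avoid.** A reader might conclude from step 1 that the margin must be absolute, or that the stated power must rest on a 25-point ECD advantage. The plan supports neither: 60% and 85% are given only as a conditional illustration, and step 5 shows other routes to 15.

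**Conclusion.** The threshold is wrong as written. It asks for more than 70 points where the plan's own figures give 25 and allow at most 40, and it does not follow from a 15% margin on either an absolute or a relative reading. This rests only on the plan's 60%, 85% and 15%.

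The −15 point threshold assumes that 15% is absolute. That is the natural reading and agrees with n=15 under the proportions formula, but the sponsor must confirm it. The 72% power figure is conditional on that formula, on a two-sided 95% CI and on exactly 15 controls; the plan allows more.

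A reader might infer that n=15 is wrong or that the study is invalid. The documents do not support this: 15 is reproducible, the error sits in one sentence, and the primary outcome is unaffected. The unstated standard deviation, sidedness and method are missing detail, not further errors.

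**What to change.** Replace the bracketed example with: *non-inferiority is concluded if the lower 95% confidence limit for the difference in mean percent time (ECD minus standard) is above −15 percentage points.* The sponsor should confirm that 15% is absolute.

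In the same edit the sponsor should state:

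- whether the limit is one-sided 95% or the lower end of a two-sided 95% CI;
- the actual basis of n=15: method, assumed true values and, if the outcome is analysed as continuous, the standard deviation;
- restated power, if the basis is the 60%/85% proportions formula and the CI is two-sided (72% with 15 per group).

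The cost is one corrected sentence and a short statement of the sample-size basis, with no extra ECD patients. The quoted power may become less favourable.

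A separate inconsistency affects the same endpoint. The Secondary outcomes section defines it as "percent of time during the goal-temperature maintenance period within 1°C of goal temperature", with goals that vary by centre from 32°C to 36°C, while the Statistical analysis section uses the study period and 33°C. Those passages must be reconciled.
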